9.3.3 Covariates

Patients recruited will be evaluated for covariates at the visit of baseline. Potential confounders include demographics (age, gender, race, and educational level), VASc score, HAS-BLED score, comorbidities, concomitant therapies, dose of dabigatran, and renal function.

If any covariate or confounding/interacting variable that may possibly influence the outcome is noted, additional analyses may be carried out to identify its effect. Details of handling covariates will be given in the statistical analysis plan (SAP), if any covariate of interest is detected.

9.3.3.1 Baseline characteristics

Demographics (date of birth, gender, race, educational level, height, weight, and alcoholic status [defined as ≥ 8 units of consumption per week])

NIS Protocol Page 28 of 46

• AF-related medical histories (date of AF diagnosis and type of AF [paroxysmal, persistent or permanent])

• Kidney function (CrCl and eGFR)

Value of serum creatinine within the allowed window (i.e., the latest data before baseline & data within \pm 6 weeks for follow-up visits) will be collected from medical chart to calculate the CrCl value by Cockcroft-Gault formula as below. $\frac{15,16}{}$

When serum creatinine is measured in mg/dL, the value is multiplied by a constant of 0.85 if the patient is female.

$$eC_{Cr} = \frac{(140 ext{ - Age}) \times ext{ Mass (in kilograms)} \times [0.85 \, if \, Female]}{72 \times ext{ Serum Creatinine (in mg/dL)}}$$

(1) When serum creatinine is measured in μ mol/L, constant is 1.23 for male and 1.04 for female.

$$eC_{Cr} = rac{(140 ext{ - Age}) \, imes \, ext{Mass (in kilograms)} \, imes \, Constant}{ ext{Serum Creatinine (in μmol/L)}}$$

- VASc score (Section 9.3.3.4)
- HAS-BLED score (Section 9.3.3.5)
- Comorbidities (Section 9.3.3.2)
- Concomitant therapies for AF or stroke prevention: Generic name or name of the therapy

9.3.3.2 Comorbidities

Comorbidities include hypertension, diabetes, congestive heart failure, vascular disease (myocardial infarction, peripheral artery disease, and complex aortic plaque), ischemic heart disease, left ventricular dysfunction, stroke, transient ischemic attack, thromboembolism, abnormal kidney function (chronic dialysis, renal transplantation, serum creatinine $\geq 200~\mu mol/L$, or eGFR $<60~mL/min/1.73~m^2$), abnormal liver function (chronic hepatic disease [e.g., cirrhosis] or biochemical evidence of significant hepatic derangement [e.g., bilirubin $>2~\times$ upper limit of normal, in association with AST/ALT/ALP $>3~\times$ upper limit normal]), major bleeding, and predisposition to bleeding/anemia.

At baseline, comorbidities will be recorded as follows according to the medical records:

■ Currently ongoing diseases: Hypertension; diabetes, congestive heart failure, left ventricular dysfunction, abnormal kidney function (chronic dialysis, renal transplantation, serum creatinine ≥ 200 μmol/L, or eGFR < 60 mL/min/1.73 m²), abnormal liver function (chronic hepatic disease [e.g., cirrhosis] or biochemical evidence of significant hepatic derangement [e.g., bilirubin > 2 × upper limit of normal, in association with AST/ALT/ALP > 3 × upper limit normal]), major bleeding, and predisposition to bleeding/anemia.

NIS Protocol Page 29 of 46

[figure not shown]
 Prior events: Vascular disease (myocardial infarction, peripheral artery disease, and complex aortic plaque) ischemic heart disease, stroke, transient ischemic attack, thromboembolism

At follow-up visits, only the current and newly onset of comorbidities since the last visit (regardless of its condition, resolved or unresolved) should be recorded on the CRF.

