9. RESEARCH METHODS

9.1 STUDY DESIGN

This is a multi-center, 1:1 randomized study to evaluate the effects of educational intervention on adherence to dabigatran, for up to 12 months. The study will be carried out at around 20 hospitals (20 ± 3), where AF patients are mainly treated in Taiwan. A total of 1,200 patients are planned to be enrolled to target 1,000 patients included in the analysis.

Patients newly diagnosed with AF within 1 month, under 75 years old, and newly prescribed with dabigatran on physician's decision per local labelling will be enrolled and equally randomized to receive standard of care (routine clinical practice) or standard of care (routine clinical practice) with advanced educational intervention. To create the randomization numbers, we will use block randomization by Statistical Analysis Software (SAS®) Version 9.4 or higher (SAS Institute, Cary, NC, USA).

The study duration consists of a 1-year enrolment period and a 12-month follow-up period consisting of visits at 3, 6, 9, and 12 months for each individual patient. Being an NIS, the time points of follow-up visits are set in accordance with the routine outpatient follow-ups of AF management in Taiwan. Patients will be continuously followed until death, lost to follow-up, or end of data collection at 12 months, whichever comes first.

The educational materials from "Shared decision making of treatment of NOAC in AF patients" (NTA: 180647) and "Atrial Fibrillation Patient Care in Hospitals" (NTA: 190707) will be used as the educational materials for the experimental group. The education materials will be delivered after randomization (baseline); and at 3, 6, and 9 months thereafter. The adherence to dabigatran will be measured by MMAS-8 score at 3, 6, 9, and 12 months.

The comorbidities, VASc score, and HAS-BLED score will be recorded at baseline; and at 3, 6, 9, and 12 months. Stroke, thromboembolic events, and bleeding-related events will also be captured during 12 months of follow-up.

The whole NIS will be implemented by a Contract Research Organization (CRO) under Local Boehringer Ingelheim's governance.

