9.2.2.2 Exclusion criteria

Patients should not be included if ANY ONE of the following criteria is met:

- (1) Contraindication to the use of dabigatran (i.e., active pathological bleeding, history of a serious hypersensitivity reaction to dabigatran [e.g., anaphylactic reaction or anaphylactic shock], severely impaired renal function [Ccr < 30 mL/min], hemorrhagic manifestations, bleeding diathesis, mechanical prosthetic heart valve, congenital or acquired coagulation disorders, organic lesions with bleeding tendency, or concomitantly use systemic ketoconazole, cyclosporine, and itraconazole)
- (2) Participate in other interventional trials currently or in the past 30 days

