9.3.3.5 HAS-BLED score

HAS-BLED¹⁸ is a scoring system developed to assess 1-year risk of major bleeding in patients with AF. The HAS-BLED score is composed of seven items with a maximum score of 9. Among all the items, 2 of them will be scored with 1 or 2 points depending on the number of corresponded description, including "abnormal renal and liver function" and "drugs or alcohol", while the other five items are counted as 1 point of each. A higher score corresponds to a greater risk of bleeding, and a score of \geq 3 points indicates "high risk". The HAS-BLED score will be calculated according to Table 3.

Table 3 Clinical characteristics composing the HAS-BLED score

Letter	Clinical Characteristic	Score
Н	Hypertension ¹	1
A	Abnormal renal function ² and abnormal liver function ³ (1 point each)	1 or 2
S	Stroke ⁴	1
В	Bleeding ⁵	1
L	Labile INRs ⁶	1
Е	Elderly, age > 65 years	1
D	Drugs or alcohol (1 point each) ⁷	1 or 2

- 1. Hypertension should be uncontrolled, with systolic blood pressure > 160 mmHg.
- 2. Abnormal kidney function is classified as a presence of chronic dialysis, renal transplantation, or serum creatinine $\geq 200 \ \mu mol/L$.
- 3. Abnormal liver function is defined as the chronic hepatic disease (e.g., cirrhosis) or biochemical evidence of significant hepatic derangement (e.g., bilirubin > 2 × upper limit of normal, in association with AST/ALT/ALP > 3 × upper limit normal, and so forth.)
- 4. Previous history, particularly lacunar.
- 5. Bleeding history, such as prior major bleeding or predisposition to bleeding (e.g., anemia).
- 6. Labile INR (e.g., therapeutic time in range < 60%).
- 7. Drugs are medication usage predisposing to bleeding (e.g. antiplatelet agents or NSAIDs). Ethanol abuse is classified as ≥ 8 units of alcoholic consumption per week.

NIS Protocol Page 31 of 46

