## Statistical Analysis Plan (SAP) for Non-Interventional Studies (NIS) BI Study Number 1160-0304

Page 20 of 27

abnormal kidney function (chronic dialysis, renal transplantation, serum creatinine  $\geq$  200 µmol/L, or eGFR < 60 mL/min/1.73 m²), abnormal liver function (chronic hepatic disease [e.g., cirrhosis] or biochemical evidence of significant hepatic derangement [e.g., bilirubin > 2 × upper limit of normal, in association with AST/ALT/ALP > 3 × upper limit normal]), major bleeding, and predisposition to bleeding/anemia.

At baseline, comorbidities will be recorded as follows according to the medical records:

- Currently ongoing diseases: Hypertension; diabetes, congestive heart failure, left ventricular dysfunction, abnormal kidney function (chronic dialysis, renal transplantation, serum creatinine ≥ 200 μmol/L, or eGFR < 60 mL/min/1.73 m²), abnormal liver function (chronic hepatic disease [e.g., cirrhosis] or biochemical evidence of significant hepatic derangement [e.g., bilirubin > 2 × upper limit of normal, in association with AST/ALT/ALP > 3 × upper limit normal]), major bleeding, and predisposition to bleeding/anemia.
- Prior events: Vascular disease (myocardial infarction, peripheral artery disease, and complex aortic plaque) ischemic heart disease, stroke, transient ischemic attack, thromboembolism

At follow-up visits, only the current and newly onset of comorbidities since the last visit (regardless of its condition, resolved or unresolved) should be recorded on the CRF.

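### Baseline major bleeding is recorded only as an ongoing disease, so a resolved prior bleed has no field of its own and that line starts at or near zero by construction

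*Protocol*

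**What the plan says.** Protocol 9.3.3.2 divides baseline comorbidities into two groups. The ongoing group opens "Currently ongoing diseases: Hypertension; diabetes, congestive heart failure, left ventricular dysfunction, abnormal kidney function" and closes with major bleeding and predisposition to bleeding or anemia. The SAP's version in 7.1.3.2 ends the same way: "major bleeding, and predisposition to bleeding/anemia". The other group reads "Prior events: Vascular disease (myocardial infarction, peripheral artery disease, and complex aortic plaque) ischemic heart disease, stroke, transient ischemic attack, thromboembolism" and has no bleeding item. The same split stands in Table 1 footnote 3 and section 9.2.3.1 of the protocol, and in Table 1 footnote 3 and section 6.2.3.1 of the SAP.

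Exclusion criterion 1 (protocol 9.2.2.2) begins "Contraindication to the use of dabigatran (i.e., active pathological bleeding" and goes on to "hemorrhagic manifestations, bleeding diathesis, mechanical prosthetic heart valve". It names neither a past major bleed nor anemia.

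HAS-BLED item B (protocol 9.3.3.5, Table 3 footnote 5) is defined by "Bleeding history, such as prior major bleeding or predisposition to bleeding (e.g., anemia". Under protocol 9.1 the "HAS-BLED score will be recorded at baseline; and at 3, 6, 9, and 12 months".

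At follow-up visits, comorbidities that are current or new since the last visit are recorded whether or not they have resolved (last paragraph of protocol 9.3.3.2 and SAP 7.1.3.2). The protocol abstract lists major bleeding among the risk factors to be described at baseline and at the end of the study. SAP section 10 gives McNemar's test at 0.05 as the general method for categorical data at baseline versus follow-up, without naming variables.

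**The concern.** The baseline field asks for something that an eligible patient should not have. The relevant baseline fact, a major bleed that has since resolved, does not bar entry but has no place on the comorbidity record. Stroke shows the contrast: it is a history item in HAS-BLED and is listed among prior events. Bleeding is also a history item in HAS-BLED, yet major bleeding is listed among ongoing diseases.

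Two things are at stake. Baseline and follow-up apply different rules to the same variable, so a rise on that line would be built in. And a patient with an old bleed who bleeds again during the study would be reported as having a newly identified risk factor.

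**Working it through.** The documents give no figure for baseline or incident major bleeding, so there is no stated result to reproduce. The check has two parts.

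**1. Recording rules for major bleeding, side by side**

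| Point | Rule | Place |
|---|---|---|
| Entry | Active bleeding and hemorrhagic manifestations excluded | Protocol 9.2.2.2 |
| Baseline comorbidity | Ongoing only; no bleeding item among prior events | Protocol 9.3.3.2, SAP 7.1.3.2 |
| Baseline HAS-BLED item B | Prior major bleeding or predisposition/anemia, one pooled point | Protocol 9.3.3.5, SAP 7.1.3.5 |
| Visit 1 bleeding-related events | Recorded if any; no look-back stated | Protocol 9.2.3.1 |
| Follow-up comorbidity | Current or new, resolved or not | Protocol 9.3.3.2, SAP 7.1.3.2 |

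Rows 1 and 2 together put the baseline line at or near zero. Row 3 captures a past bleed but cannot tell it from anemia. Row 4 is not a history field, because protocol 9.3.2.6 places these events in the 12 months of follow-up. Row 5 is wider than row 2.

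For scale only: if 2% to 8% of patients had a past major bleed (an assumption with no support in the documents), 1,200 × 0.02 = 24 to 1,200 × 0.08 = 96 enrolled patients would show none on this line.

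**2. What a paired test would do with a zero baseline**

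No patient can move from yes to no, so the discordant counts are 0 and c, where c is the number of new cases.

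- Exact two-sided p = 2 × 0.5^c. For c = 5, p = 0.0625; for c = 6, p = 0.031.
- Asymptotic chi-square = c on 1 degree of freedom. For c = 3, p = 0.083; for c = 4, p = 0.0455.
- Continuity-corrected chi-square = (c − 1)²/c. For c = 5, 16/5 = 3.2 and p = 0.074; for c = 6, 25/6 = 4.17 and p = 0.041.

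The SAP does not say which form it would use. The threshold is therefore 4 new cases (asymptotic) or 6 (exact or corrected). Taking c as binomial with n = 1,000 (the completers expected in protocol 9.5) and an assumed 12-month incidence, and counting any new major bleed during follow-up as present at the end:

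| Assumed incidence | Chance of at least 4 | Chance of at least 6 |
|---|---|---|
| 0.3% | 35% | 8% |
| 0.5% | 74% | 38% |
| 1% | 99% | 93% |
| 2% | about 100% | about 100% |

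If end-of-study status meant only the last visit interval, c would be smaller. The visible text does not settle this.

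**The case against.** The strongest reply is that the history is not lost. HAS-BLED has its own row in Table 1, is taken at baseline, and item B covers prior major bleeding in terms. This stands: a reader might infer from the comorbidity list that prior major bleeding is never captured, and the documents do not support that. What remains is that the single point pools two things. Also, the steps listed for acquiring HAS-BLED in protocol 9.2.3.1 (laboratory values, dialysis or transplant, medication) include no bleeding history, so the source of item B is not named.

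A reader might also infer that HAS-BLED is a point too low and that some patients fall below the high-risk cut of 3. That needs item B to be derived from the comorbidity field, which neither document says. Table 3 suggests separate scoring: its hypertension item requires systolic pressure above 160 mmHg, and its renal item omits the eGFR criterion that the comorbidity list includes. A chart-scored item B would not contradict the comorbidity field either, since a patient can have a past bleed and no ongoing one.

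Nor does every bleeding comparison start at zero. Anemia is not an exclusion, HAS-BLED is not forced to zero, and bleeding-related events are a separate follow-up outcome, already classed as major or minor (protocol 9.3.2.6) and described in the pooled set (9.7.1).

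Finally, the outcome concerns newly identified risk factors, so counting new bleeds upward is partly the intent. Protocol 9.7.1 makes further outcomes descriptive, and the general McNemar sentence names no variable. This is fair: a paired test of this line cannot be confirmed from the public text, so the calculation above is conditional. The unequal recording rules remain in a purely descriptive table.

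**Conclusion.** The point holds for one line, the baseline major-bleeding comorbidity. Followed as written, it is at or near zero by construction, and its change to the end of the study would largely reflect how baseline was recorded. The qualifier is needed because no definition or look-back is given for the baseline entry, so a site could enter a recent bleed; that would be inconsistent recording, not a remedy.

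Under-scoring of HAS-BLED is conditional on two things: item B being derived from this field, and predisposition/anemia not already scoring the point. The p-value thresholds hold only if the McNemar rule is applied to this line, and the incidence and prevalence ranges are assumptions.

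Predisposition/anemia, the bleeding-event outcome and the MMAS-8 primary endpoint are not affected. Severity: minor.

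**What to change.** 1. List prior major bleeding among the prior events in protocol Table 1 footnote 3, 9.2.3.1 and 9.3.3.2, and in the matching SAP text (Table 1 footnote 3, 6.2.3.1 and 7.1.3.2).
2. State that this field, or predisposition/anemia, feeds HAS-BLED item B.
3. Report follow-up major bleeding as incidence, separately from baseline history, and exclude this line from any paired baseline-versus-end test.

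The cost is a wording change in two documents and the label of one CRF field. The source is the medical record already being abstracted at baseline. The change concerns data capture and reporting only.

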9.3.3.3 Concomitant therapy

The study will collect two types of concomitant therapies, including (1) therapies related to the calculation of HAS-BLED score and (2) therapies for AF or stroke prevention. These therapies will be collected according to the plan as below:

- (1) Therapies related to HAS-BLED score include chronic dialysis or renal transplant due to abnormal renal function & medication usage predisposing to bleeding (antiplatelet agents or NSAIDs).
- Baseline: Chronic dialysis or renal transplant prior to baseline will be collected, while medication usage predisposing to bleeding within 1 month prior to baseline will be collected.
- Follow-up visits at every 3 months: Used during the interval of visits will be collected
- (2) Therapies for AF or stroke prevention:
- Baseline: Used within 1 month prior to the enrolment will be collected at baseline.
- Follow-up visits at every 3 months: Changes in concomitant therapies will be collected.

V	Vascular disease (prior myocardial infarction, peripheral artery disease, or aortic plaque)	1
A	Age 65 – 74 years	1
Sc	Sex category (i.e., female sex)	1

9.3.3.5 HAS-BLED score

HAS-BLED¹⁸ is a scoring system developed to assess 1-year risk of major bleeding in patients with AF. The HAS-BLED score is composed of seven items with a maximum score of 9. Among all the items, 2 of them will be scored with 1 or 2 points depending on the number of corresponded description, including "abnormal renal and liver function" and "drugs or alcohol", while the other five items are counted as 1 point of each. A higher score corresponds to a greater risk of bleeding, and a score of \geq 3 points indicates "high risk". The HAS-BLED score will be calculated according to Table 3.

Table 3 Clinical characteristics composing the HAS-BLED score

Letter	Clinical Characteristic	Score
Н	Hypertension ¹	1
A	Abnormal renal function ² and abnormal liver function ³ (1 point each)	1 or 2
S	Stroke ⁴	1
В	Bleeding ⁵	1
L	Labile INRs ⁶	1
Е	Elderly, age > 65 years	1
D	Drugs or alcohol (1 point each) ⁷	1 or 2

- 1. Hypertension should be uncontrolled, with systolic blood pressure > 160 mmHg.
- 2. Abnormal kidney function is classified as a presence of chronic dialysis, renal transplantation, or serum creatinine $\geq 200 \ \mu mol/L$.
- 3. Abnormal liver function is defined as the chronic hepatic disease (e.g., cirrhosis) or biochemical evidence of significant hepatic derangement (e.g., bilirubin > 2 × upper limit of normal, in association with AST/ALT/ALP > 3 × upper limit normal, and so forth.)
- 4. Previous history, particularly lacunar.
- 5. Bleeding history, such as prior major bleeding or predisposition to bleeding (e.g., anemia).
- 6. Labile INR (e.g., therapeutic time in range < 60%).
- 7. Drugs are medication usage predisposing to bleeding (e.g. antiplatelet agents or NSAIDs). Ethanol abuse is classified as ≥ 8 units of alcoholic consumption per week.

NIS Protocol Page 31 of 46

9.4 DATA SOURCES

As this is an NIS, no diagnostic or monitoring procedures additional to the standard of care and routine practice (except for the additional education delivered to the experimental group) will be applied to the patients. All the assessment will be performed by the investigator if they are deemed necessary for the medical treatment procedure.

This study will collect the data from medical charts and MMAS-8 questionnaires. Investigators or delegated site staffs will record the data on the CRF. Data source includes questionnaires, hospital discharge files, abstracts of primary clinical records, electronic medical records, clinical databases, administrative records such as eligibility files, prescription drug files, biological measurements, exposure/work history record reviews, etc.

9.5 STUDY SIZE

Approximately 1,200 patients from around 20 hospitals (20 ± 3) will be enrolled in this study. Assuming a drop-out rate of 20%, it is expected to have 1,000 patients completing the study. The sample size is determined based on the feasibility, planned enrolment period, number of potential patients at selected sites, and expected precision of the estimates. As the selected sites are the hospitals with most AF patients treated with dabigatran in Taiwan from northern to southern areas, the patients recruited into this study will be the representative of the AF population treated with dabigatran and the healthcare settings in Taiwan.

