9.2 SETTING

The study is planned to be carried out at around 20 hospitals (20 ± 3), where AF patients are mainly treated in Taiwan. A total of 1,200 patients will be enrolled to have 1,000 patients included in the analysis.

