9.7 DATA ANALYSIS

Analyses will be performed by a designated CRO. The main analysis population will consist of all eligible patients (i.e., all patients who have signed the informed consent and fulfilled all inclusion criteria and no exclusion criteria).

Analytic specifications, including tables and listings, will be detailed in the statistical analysis plan (SAP) that is separate from the full study protocol. A change to the data analysis methods described in the study protocol will require an amendment only if it changes a principal feature of the study objective. Additional exploratory analyses of the data will be conducted as deemed appropriate.

All statistical assessments will be performed using Statistical Analysis Software (SAS®) Version 9.4 or higher (SAS Institute, Cary, NC, USA).

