9.7.1 Main analysis

The analyses will be mainly descriptive to gain an understanding of the characteristics of the sample studied.

Continuous variables will be reported as number, mean, standard deviation (SD), minimum, maximum, and 95% confidence interval (CI). Categorical variables will be summarized as number and frequency or percentage with observed (non-missing) data.

Analysis of endpoints:

- The primary outcome is to describe the proportion of patients with high adherence to dabigatran treatment which is defined as achieving MMAS-8 score of 8 points at 12 months for each group. Subjects without MMAS-8 value recorded at 12 months will be excluded from the analysis of primary endpoint.
- The Mean MMAS scores at 3, 6, 9 and 12 months will be compared between patients with and without advanced educational intervention using Chi-square, Fisher's exact, or other appropriate tests for categorical data and using t-test or Wilcoxon rank-sum test for continuous data. Similarly, subjects without MMAS-8 value recorded at a specific visit will be excluded from the analysis of corresponding secondary endpoints.
- Other secondary outcomes in patients with and without advanced educational intervention separately and further outcomes only within pooled patient set (e.g., comorbidities, stroke/thromboembolic/bleeding events, risk factors, ADR, etc.) will all be analyzed in a descriptive manner
- All tests will be done under a statistical level of 0.05.

NIS Protocol Page 33 of 46

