#### 9.2 Handling of Missing Values

No imputation method will be performed to estimate the missing values for all the study variables.

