#### 10. DATA ANALYSIS

The main and further analysis population will consist of all eligible patients (i.e., all patients who have signed the informed consent and have fulfilled all eligibility criteria).

Continuous variables will be reported as number, mean, standard deviation (SD), minimum, maximum, and 95% confidence interval (CI). Categorical variables will be summarized as number and frequency or percentage with observed (non-missing) data. Missing numbers of both continuous and categorical variables will also be summarized.

As for comparisons of continuous data between baseline and follow-up visit, paired-t test will be performed at the significant level of 0.05. Shapiro—Wilk test will be performed to test the normality of data. When normality assumption is violated, Wilcoxon signed-rank test will be performed instead. On the other hand, McNemar's test will be performed to for comparisons of categorical data between baseline and follow-up visit at the significant level of 0.05.

For the endpoints pre-identified to compare between patients with and without advanced educational intervention, the analyses will be done by independent t-test for continuous data at the significant level of 0.05. Shapiro–Wilk test will be performed to test the normality of data. When normality assumption is violated, Wilcoxon rank-sum test will be performed instead. On the other hand, Chi-square or Fisher's exact test will be performed to for comparisons of categorical data at the significant level of 0.05.

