#### 10.1 Main analysis

The primary outcome is to describe the proportion of patients with high adherence to dabigatran treatment which is defined as achieving MMAS-8 score of 8 points at 12 months for each group.

• The proportion of patients with high (MMAS-8 score: 8 points) adherence to dabigatran treatment at x months ( $P_{H,x}$ ) is defined as following formula:

$$P_{H,x} = \frac{\text{Number of subjects with 8 points of MMAS} - 8 \text{ score at x months}}{\text{Number of subjects at x months}}$$

Subjects without MMAS-8 value recorded at 12 months will be excluded from the analysis of primary endpoint. The Chi-square test or Fisher's exact test will be used to test the equality between two study groups.

The secondary analyses are described below:

- (1) The proportion of patients with high (MMAS-8 score: 8 points) adherence to dabigatran treatment at each visit (3, 6, and 9 months),
- (2) The proportion of patients with medium (MMAS-8 score: 6-7 points) and low (MMAS-8 score < 6 points) adherence to dabigatran treatment at each visit (3, 6, 9 and 12 months),
- (3) The mean MMAS-8 score at each visit (3, 6, 9 and 12 months) and
- (4) The discontinuation rate of dabigatran and reasons for discontinuation (switch or stop treating dabigatran).

Similar as primary endpoint, Chi-square test or Fisher's exact test will be used to test the equality of MMAS-8 score, discontinuation rate and reasons for discontinuation between two

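### The planned enrolment, drop-out rate and number of completers do not agree: 1,200 enrolled with 20% drop-out gives about 960 completers, not 1,000

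*Protocol*

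**What the plan says.** Protocol 9.5 and the study-size entry of the abstract (Protocol 4) give approximate enrolment of 1,200 from around 20 hospitals, followed by: "Assuming a drop-out rate of 20%, it is expected to have 1,000 patients completing the study". Protocol 9.5 bases the size on feasibility, the enrolment period, the number of potential patients at the sites and the expected precision of the estimates. It gives no power, effect size or numerical precision target.

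The same pair of numbers appears elsewhere without a drop-out rate. Protocol 9.1 has "A total of 1,200 patients are planned to be enrolled to target 1,000 patients included in the analysis", and Protocol 9.2 has "A total of 1,200 patients will be enrolled to have 1,000 patients included in the analysis". SAP 6.1 and 6.2 repeat both statements.

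The analysis sections define who is analysed differently again:

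- Protocol 9.7: "The main analysis population will consist of all eligible patients". SAP 10 says the same for the main and further analyses.
- Protocol 9.7.1, for the primary endpoint: "Subjects without MMAS-8 value recorded at 12 months will be excluded from the analysis of primary endpoint". SAP 10.1 agrees.
- SAP 9.2: "No imputation method will be performed to estimate the missing values for all the study variables".

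**The concern.** Enrolment, drop-out and completers are tied by one equation, so any two fix the third. The plan states all three together, and they do not fit. A reader who takes the drop-out assumption at face value will expect 960 completers; one who takes the 1,000 will assume a lower drop-out than the plan states.

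The 1,000 also does not count the same thing throughout. It is patients completing in Protocol 9.5 and the abstract, and patients in the analysis in Protocol 9.1 and 9.2 and SAP 6.1 and 6.2. Neither is the main analysis population, which is all eligible patients, and neither is exactly the primary-endpoint denominator, which is patients with a 12-month MMAS-8 score.

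What is at stake is modest. Protocol 9.5 names expected precision as one basis for the size, and precision depends on the number analysed. The study-size section is where that number is looked up, and the number there does not follow from its own assumption.

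**Working it through.** **Inputs**

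- Enrolled, N = 1,200 (Protocol 9.5 and abstract; also 9.1, 9.2; SAP 6.1, 6.2)
- Drop-out, d = 0.20 (Protocol 9.5 and abstract)
- Stated completers, n = 1,000 (Protocol 9.5 and abstract)
- Allocation 1:1 (Protocol 9.1)
- High adherence, p: 0.71 is the US dabigatran figure in Protocol 7; 0.50 is an assumption, used as the least favourable value

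**Reproducing the plan's figure**

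Completers = N × (1 − d) = 1,200 × 0.80 = **960**. The stated 1,000 is not reproduced; the gap is 40, or 40/1,000 = 4.0%.

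Solving for each of the other two:

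- Enrolment needed for 1,000 completers: n/(1 − d) = 1,000/0.80 = **1,250**, which is 50 more than stated (50/1,200 = 4.2%).
- Drop-out implied by 1,200 and 1,000: 1 − 1,000/1,200 = **16.7%**.

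The pair is matched by 1,000 × 1.20 = 1,200, which suggests that 20% was added to the target where the target should have been divided by 0.80. The documents do not show the calculation, so this is an inference, and the finding does not depend on it.

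**Effect on precision**

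The 95% half-width for the difference between two proportions, with the same p in both arms and m patients per arm, is 1.96 × √(2p(1 − p)/m). For example, at p = 0.71 and m = 480: 1.96 × √(2 × 0.71 × 0.29/480) = 5.74 points.

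| Analysed in total (per arm) | p = 0.50 | p = 0.71 |
|---|---|---|
| 1,000 (500), as stated | 6.20 | 5.62 |
| 960 (480), at 20% drop-out | 6.33 | 5.74 |
| 912 (456), a further 5% without a 12-month score | 6.49 | 5.89 |
| 864 (432), a further 10% without a 12-month score | 6.67 | 6.05 |

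Half-widths are in percentage points. Moving from 500 to 480 per arm costs 0.12 to 0.13 points. The last two rows assume that 5% or 10% of completers have no 12-month MMAS-8 score (960 × 0.95 = 912; 960 × 0.90 = 864). The plan gives no such rate. The rows show only why 960 is a ceiling for the primary endpoint.

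**The case against.** The best defence is that nothing turns on the 1,000. The size is set by feasibility, the analyses are described as mainly descriptive, and no power or numerical precision target uses the figure. That is correct, and it is why the point is minor. It does not make the stated figure right.

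A second argument is that enrolment is only approximate. The number of hospitals is 20 ± 3; at 1,200/20 = 60 patients per site, 17 to 23 sites would give 1,020 to 1,380 patients, a range that contains 1,250. But Protocol 9.1 and 9.2 and SAP 6.1 and 6.2 give a total of 1,200 without qualification. Uncertainty about the number of sites also does not alter the expected number of completers at the nominal enrolment.

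Third, completing and being included in the analysis can be read as nearly the same group, because the primary endpoint needs a 12-month score. This has some force for the primary endpoint. It does not fit the main population of all eligible patients, nor a completer without a recorded score.

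Fourth, 480 per arm assumes that all 1,200 are randomised and that drop-out is equal in the two arms. Protocol 9.2.3 counts a patient as enrolled once consent is signed, and eligibility is assessed after that at the baseline visit, so consented screen failures could fall within the 1,200. Protocol 9.1 and 9.2.2, however, describe enrolled patients as eligible and randomised. The per-arm figure therefore stands as nominal.

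**Conclusion.** The concern holds. The three figures in Protocol 9.5 and the abstract are inconsistent, and no other section of either document reconciles them. At 1,200 enrolled and 20% drop-out, expected completers are about 960, which is 40 (4%) below the stated 1,000. The other four sections are not separate errors, because they state no drop-out rate, but they depend on whichever figure is changed.

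Severity is minor: the loss of precision is about 0.1 percentage point over the range of p examined. The 960 rests only on the plan's own enrolment and drop-out figures. The 480 per arm also assumes that all enrolled patients are randomised and that drop-out is equal by arm. For the primary endpoint, 960 is an upper figure, because missing 12-month scores are excluded and not imputed.

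**What to change.** Reconcile the figures in Protocol 9.5 and the abstract in one of three ways:

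- **Keep 1,200 and 20%**, and restate expected completers as about 960 (nominally 480 per arm). This is the cheapest: no change to enrolment, and a slightly less favourable number.
- **Keep 1,200 and 1,000**, and justify a drop-out of about 16.7%.
- **Keep 20% and 1,000**, and raise enrolment to 1,250, at the cost of 50 more patients.

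Whichever is chosen, bring Protocol 9.1 and 9.2 and SAP 6.1 and 6.2 into line, and say what the number counts: at most the patients available for the 12-month primary endpoint, not the all-eligible main population. This is wording in six places, four of them in the protocol. If the protocol text is changed by amendment, the approvals in Protocol 10.1 apply, so the correction could travel with the next amendment.

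A separate, optional addition: for the primary proportion, the visible text of SAP 10.1 plans only a test ("The Chi-square test or Fisher's exact test will be used to test the equality between two study groups"), and SAP 10 lists a 95% confidence interval for continuous variables but not for categorical ones. Unless the mock-up tables mentioned in SAP 3 already include them, add 95% confidence intervals for each arm's proportion with high adherence at 12 months and for the difference. That is three intervals in one table.
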